5.5 Summary of study procedures

Table 6. Summary of study procedures

Participant group	List of study procedures	Estimated time	Data collection forms used
Health workers	
 • Training on the use of POC G6PD tests • Consent and enrolment • Usability assessment questionnaire 	
 • Up to 5 hours • 20 minutes • 20 minutes 	
 • Appendix A2
Children aged 2-18	
 • Assent, parental permission, and enrollment • Conduct POC tests and blood draw 	
 • 20 minutes • Up to 30 min 	
 • Appendix A1
Adults	
 • Consent and enrolment • Conduct POC tests and blood draw 	
 • 20 minutes • Up to 30 min 	
 • Appendix A1

Figure 3. Participant flow and follow-up procedures

*Vivax positive patients, recruited from the enriched sample of participants known to be G6PD deficient or intermediate, may receive a false negative G6PD normal result from the investigational POC test. In the event this occurs, this subpopulation will be considered G6PD intermediate/deficient and provided counseling and a counselling card as described in section 5.4.

5.6 Standard care and study procedures

In Brazil, national guidelines for *P. vivax* malaria call for treatment of the blood stage of the parasite. For the prevention of relapse, the guidelines recommend treatment that includes 3 days of chloroquine (CQ) and then 7 days of primaquine (PQ). As part of standard malaria case management, suspected malaria cases are confirmed with microscopy. No G6PD testing is recommended or routinely available prior to treatment with primaquine.

In Brazil, anemia screening is not routinely done at the point of care as part of case management for suspected malaria. The thresholds for anemia are as follows:

- Mild anemia:
 - Hb 10.0 – 11.9 g/dl in women
 - Hb 10.0 – 10.9 in pregnant women and children
 - Hb 10.0 – 12.9 g/dl in men
- Moderate anemia: Hb 7.0 – 9.9 g/dl
- Severe anemia: Hb <7.0 g/dl

There are no national guidelines regarding the treatment of anemia in Brazil. Treatments provided at the discretion of the medical care provider and generally involves iron supplementation, using oral iron tablets or parenteral injections, depending on severity. In this study, all diagnoses and treatment of anemia will be done through referral to a health agent or clinic.

For the research study, in addition to conducting microscopy to screen for malaria, the study will test participants using an investigational POC G6PD test, an approved hemoglobinometer, and laboratory reference assays intended to assess the performance of the POC tests. Participants who test positive for malaria will be referred to a local health agent for further testing and case management. All treatment decisions will be made through referral to a local health worker or clinic.

If any participants are confirmed *P. vivax* malaria positive and G6PD deficient at the point of care, the study team will relay this the information as part of the counselling. The study team will refer the participant to a health for treatment, equipped with counselling information that the participant may be G6PD deficient or intermediate and if given primaquine treatment is at an increased risk of severe hemolysis. This will enable the participant to receive immediate treatment for the blood stage infection and provide better information to the health worker responsible for case management, including any treatment for the liver stage infection. The participant's G6PD status will then be confirmed by a reference assay to inform further case management as necessary. The table below outlines the study procedure and subsequent follow up action.

Table 5. Case management

Study test	Result		Action
Hemoglobin	Normal hemoglobin levels (by national guidelines)		No action
	Mild moderate or severe anemia (by national guidelines)		Counselling re: the results of the hemoglobin test and referral to the health system for follow-up case management. This may involve the provision of iron tablets or other treatment depending on severity.
G6PD deficiency	Negative test result on investigational device (G6PD normal)		No immediate action. If reference assay is discrepant and identifies G6PD intermediate or deficient status, the study team will conduct follow-up counselling (Appendix C2).
	Positive test result on investigational device (G6PD deficient or intermediate)		Result to be confirmed at the laboratory with the reference assay. If confirmed G6PD deficient or intermediate with the reference assay, the study team will conduct follow-up counselling (Appendix C2).
Malaria	Negative test result (no malaria)		G6PD and hemoglobin managed as above, otherwise no action
	Positive test result (confirmed malaria)	POC G6PD normal	Patient referred to health system for free treatment: 3 days CQ and 7 days PQ. If confirmed deficient or intermediate with reference assay, provide follow up counselling as described above.
		POC G6PD intermediate	Patient referred to health system for free treatment: 3 days CQ and 7 days PQ. Provide counseling re: G6PD intermediate status and recommend additional monitoring and attention to possible signs/symptoms of hemolysis. If confirmed deficient or intermediate with reference assay, provide follow up counselling as described above.
	POC G6PD deficient		Patient referred to health system for free 3 days CQ with recommendation for health care provider to withhold PQ until confirmatory G6PD testing. Based on the reference assay, provide appropriate counselling for G6PD status as well as for any future treatment with PQ.

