If the results of the reference assay confirm the results of the POC G6PD test (enzymatic activity less than 30%) they will be contacted and informed of the result and their G6PD status by validated reference assay. If the results of the reference assay indicate that the participant is G6PD normal, they will be contacted, informed of the result, and referred to a health agent to receive with standard treatment for liver stage disease, as per national guidelines.

Participants found to be vivax positive and G6PD intermediate

For vivax positive participants found to be G6PD intermediate with the POC test (G6PD test result between 30 and 80% of normal enzymatic activity), the study team will provide referral with the recommendation that primaquine treatment be closely monitored for signs of hemolysis given the increased risk of hemolysis associated with moderate G6PD deficiency.

If the results of the reference assay confirm the results of the POC G6PD test (enzymatic activity between 30-80%) they will be contacted and informed of the result and their G6PD status by validated reference assay. If the results of the reference assay indicate that the participant is G6PD normal, they will be contacted and informed of the result and referred to a health agent to receive with standard treatment for liver stage disease, as per national guidelines.

Among any vivax positive participants, those known to be G6PD intermediate or deficient based on previous studies may receive a false negative result on the POC investigational test in this study and found to be G6PD normal. In the event that this occurs, the study team will proceed in the same manner as for participants found to be vivax positive and POC G6PD deficient or intermediate. See Figure 3.

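### Table 5 omits the exception in section 5.4 and the Figure 3 footnote for vivax-positive participants already known to be G6PD deficient or intermediate who read normal on the POC test

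*Combined protocol and SAP*

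**What the plan says.** Section 5.4 (Test result return and follow up) foresees that a vivax-positive participant known from earlier surveys to be deficient or intermediate may read normal on the investigational test. In that event "the study team will proceed in the same manner as for participants found to be vivax positive and POC G6PD deficient or intermediate". The footnote to Figure 3 (section 5.5) repeats the rule: "this subpopulation will be considered G6PD intermediate/deficient and provided counseling and a counselling card", with a reference back to section 5.4.

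Table 5 (section 5.6) is introduced with the words "The table below outlines the study procedure and subsequent follow up action". Two of its rows cover a normal POC result:

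- In the malaria block, labelled "Positive test result (confirmed malaria)", the action for a POC-normal participant is "Patient referred to health system for free treatment: 3 days CQ and 7 days PQ", followed by "If confirmed deficient or intermediate with reference assay, provide follow up counselling as described above".
- In the general G6PD block, the action for a normal result begins "No immediate action. If reference assay is discrepant and identifies G6PD intermediate or deficient status", and counselling then follows.

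Neither row mentions prior known status or refers to section 5.4.

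On species, the text of section 5.6 gives the regimen under the national guidance for *P. vivax*: "the guidelines recommend treatment that includes 3 days of chloroquine (CQ) and then 7 days of primaquine (PQ)". The pathways in section 5.4 are also written for vivax-positive participants.

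**The concern.** The protocol gives two instructions for the same person. The situation is foreseen: section 4.1 plans to draw about half the participants from people whose G6PD status is already known, and the protocol twice anticipates false normal readings among those known to be deficient or intermediate. At stake is what the study team tells the participant and the treating health worker before the reference result is available. For a known-deficient participant, that includes the recommendation on primaquine.

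The missing species label raises a smaller issue of the same kind. A participant with non-vivax malaria falls into rows whose regimen and G6PD advice the text ties to *P. vivax*.

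**Working it through.** The check is mainly a comparison of text. The plan states no figure to reproduce.

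**Step 1. Vivax positive, POC normal, status already known.**

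| Known status | Section 5.4, with Figure 3 footnote | Table 5, POC-normal malaria row |
|---|---|---|
| Deficient | Referral with a recommendation to withhold primaquine until confirmatory testing (at most one week); handled and counselled as deficient | Referral for CQ and PQ; counselling only after the reference assay |
| Intermediate | Referral with a recommendation of close monitoring for hemolysis; handled and counselled as intermediate | Referral for CQ and PQ; no monitoring recommendation; counselling only after the reference assay |

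The first line conflicts on the primaquine recommendation. The second does not conflict on the regimen, since Table 5 gives the same CQ and PQ referral in its POC-intermediate row and section 5.4 recommends monitoring rather than withholding. It conflicts on immediate counselling and monitoring advice. The table assumes that known-deficient participants follow the deficient path and known-intermediate participants the intermediate path. Section 5.4 does not spell this out, but it is the natural reading.

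**Step 2. The general G6PD row.** Its instruction of no immediate action is not limited to participants without malaria, so read literally it also covers the person in step 1. The exception in section 5.4 is confined to vivax-positive participants. For known-status participants without vivax malaria, there is no conflict over the exception.

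**Step 3. Species.** Section 5.4 requires confirmatory testing before participants without *P. vivax* are told of a deficient or intermediate result. Table 5's POC-intermediate row provides counselling on intermediate status, on the POC result, to any confirmed malaria case. For non-vivax malaria the two differ on when the result is disclosed. Section 1.0 also describes *P. falciparum* as treated differently from *P. vivax*, and Table 5 has no row for it.

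**Step 4. How often could this arise?** The number is (known deficient or intermediate participants enrolled) × (proportion vivax positive) × (proportion of those reading POC normal). The documents give neither of the first two for the known-status sample, so no count follows. Table 7 (section 7.1) indicates the likely mix:

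- At the 30% threshold, sensitivity is 100% (95.1 to 100.0). No deficient sample was missed, and the interval allows a miss rate of up to 100 − 95.1 = 4.9%.
- At the 80% threshold, the printed sensitivity is 86% (80.7 to 93.9), so 100 − 86 = 14% of samples below 80% activity were read as normal. The printed interval is the exact one for 92 of 104, which is 88.5% (11.5% missed), so the estimate and interval do not quite agree.
- With no misses below 30%, the misses at the 80% threshold lie between 30% and 80% activity. That is the intermediate band, where the conflict concerns counselling and monitoring only.

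These are laboratory data at ROC-optimised cutoffs under temperature and humidity stress. They show the direction but not the rate to expect in the field.

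**The case against.** The best answer is that Table 5 is organised by study test result and has no column for prior status. The specific exception is stated twice elsewhere and can be read as qualifying the general row, so what is missing is a cross-reference. That is a fair account of the probable intent. It does not remove the literal difference: the table is introduced as outlining the study procedure, and its rows cover every POC-normal case without qualification.

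It can also be said that the study team does not prescribe, since section 5.6 leaves treatment decisions to the local health worker or clinic. That stands, and it limits the point to the referral recommendation and the counselling. Those are the study team's own actions, and they are what differ.

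On species, the paragraph before Table 5 speaks of *P. vivax*, so the row label may be shorthand. This is why the species point is the lesser one. The difference over disclosure remains.

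A reader might infer more than the documents support:

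- That half the sample is exposed. Section 4.1 says about half have known status, not known deficient or intermediate status. About 300 of the 2,000 participants (200 intermediate, 100 deficient) are expected in those two groups overall.
- That staff will work from Table 5. The protocol does not say so. Section 5.4 has staff return malaria and anemia results from a script in Appendix C3, which is not available here.
- That the table takes away a safeguard for a countable number of people. The false normals in Table 7 fall in the intermediate band, where both passages lead to referral for CQ and PQ, and vivax positivity in the known-status group is not given.

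**Conclusion.** The inconsistency is real and narrow. Table 5 lacks the known-status exception in section 5.4 and the Figure 3 footnote. For a vivax-positive, known-deficient participant who reads POC normal, the literal instructions differ on whether the referral carries a recommendation to withhold primaquine for up to one week pending confirmation. For a known-intermediate participant they differ only on immediate counselling and monitoring advice. The unlabelled malaria rows are a secondary ambiguity, with one actual difference over disclosing a POC result to participants without *P. vivax*.

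The number affected cannot be computed. It is probably small and mostly intermediate, if the laboratory performance in Table 7 carries over to the field. Only the footnote to Figure 3 could be checked, because the figure itself is not shown. The footnote reaches the primaquine recommendation only through its reference to section 5.4. The point concerns consistency of procedure and has no bearing on the accuracy analysis.

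**What to change.** Reconcile both POC-normal rows of Table 5 (the malaria row and the general G6PD row) with section 5.4 and the Figure 3 footnote, so that one stated pathway applies to vivax-positive participants with known deficient or intermediate status. State explicitly whether known-deficient and known-intermediate participants follow separate paths. Reconcile the species-free row label with the vivax-only text in sections 5.4 and 5.6, and with the requirement in section 5.4 for confirmation before participants without *P. vivax* are told their G6PD result. Check the result-return script in Appendix C3 against the reconciled text. The investigators should decide which rule stands; this review takes no position on that.

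The cost is the wording of one table, matching changes to training material, and submission of the amendment to the review boards under section 10.4. Sample size and analysis are unaffected.

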- Point-of-care
- Easy-to-use
- Affordable
- Reviewed by WHO Prequalification Programme (WHO PQ)

PATH and the product developers have assessed POC test performance through laboratory evaluations using frozen specimens. Next steps in the validation of the POC tests include an assessment of diagnostic accuracy using clinical samples in target geographies. In addition to diagnostic accuracy, there is a need to assess the POC test to ensure its suitability for use among target end users. Data on both diagnostic performance and test usability will be required to support the registration of POC G6PD tests with key regulatory authorities in target countries.

In Brazil, there is no routine screening to identify individuals with G6PD deficiency in the public health system and treatment with primaquine is recommended for all persons infected with *P.vivax*, with the exception of pregnant women and children less than six months of age [11-12]. In a recent cost study, Peixoto et al. estimate that the use of primaquine among the population with G6PD deficiency represents a great burden for the public health system on Brazil [13].

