4.2 Inclusion and exclusion criteria

4.2.1 Participant with unknown G6PD status

Inclusion criteria:

- Seeking care at the Manaus or Porto Velho clinics
- 2 years age or older
- Willing to provide informed consent

Exclusion criteria

- Younger than 2 years of age
- Participants who received a blood transfusion in the last 3 months, self-report
- Unwilling to provide informed consent

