5.4 Test result return and follow up

Results of point of care malaria microscopy will be returned to participants as per standard care. Results of the POC hemoglobin testing will be returned to participants

immediately after testing, as the test is registered for use in Brazil. Study staff will relay results and counsel participants who test positive for malaria or anemia according to the results return script (Appendix C3). Any participants identified as malaria positive or anemic will be counselled and referred for follow-up. Participants in the clinic will receive standard care at the clinic and participants recruited through household surveys will be referred for follow-up to the local health agent as per routine practice.

In Brazil, no routine screening to identify individuals with G6PD deficiency is implemented in the public health system and treatment with primaquine is recommended for all people infected with *P. vivax* with the exception of pregnant women and children under six months of age. However, information regarding the G6PD status of a vivax patient is critical for informing safe and effective treatment recommendations. As per WHO guidelines for the treatment of malaria, standard treatment of primaquine should not be given to patients who are G6PD deficient in order to avoid primaquine-induced hemolysis and patients who are G6PD intermediate should be monitored closely for signs of hemolysis [18].

Initial evaluations by PATH indicate that the POC G6PD test is able to identify G6PD deficiency (see section 7.1). As such, participants who test positive for *P. vivax* malaria and are found to be G6PD deficient or intermediate will be notified of their POC test result in order to make that information available to their health provider when determining their course of treatment for vivax malaria.

Participants found to be vivax positive and G6PD deficient

For vivax positive participants found to be G6PD deficient with the POC test (G6PD test result of below 30% of normal enzymatic activity), the study team will provide referral with the recommendation that primaquine treatment be withheld until confirmatory testing can be completed. Confirmatory testing will take no more than one week to complete. At that time, through referral to the health agent, *P. vivax* patients who are identified as G6PD deficient can receive treatment for the blood stage disease (treatment with chloroquine) immediately.

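### Table 5 names a primaquine course for malaria-positive participants without the pregnancy exception stated elsewhere in the protocol, and pregnancy is not an exclusion

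*Combined protocol and SAP*

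**What the plan says.** All references are to the combined protocol and SAP.

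- **The exception.** Section 1.0 says primaquine is recommended in Brazil for everyone infected with *P. vivax*, "with the exception of pregnant women and children less than six months of age". Section 5.4, which governs the return of results, repeats it: "with the exception of pregnant women and children under six months of age".
- **The referral rows.** In Table 5 (section 5.6), the entry for confirmed malaria with a normal POC G6PD result begins "Patient referred to health system for free treatment: 3 days CQ and 7 days PQ". The entry for an intermediate result begins "Patient referred to health system for free treatment: 3 days CQ and 7 days PQ. Provide counseling re: G6PD intermediate status". Neither mentions pregnancy. The summary of the national guideline that precedes the table names the same course and also omits the exception.
- **The accompanying message.** For vivax-positive, POC-intermediate participants, section 5.4 has the study team recommend close monitoring of primaquine treatment for hemolysis.
- **Eligibility.** In section 4.2.1 the exclusions are age under 2 years, unwillingness to consent, and "Participants who received a blood transfusion in the last 3 months, self-report". Section 4.2.2 has the same list, with assent and unavailability at the visit added. Pregnancy appears in neither.
- **Anemia bands.** Section 5.6 gives a separate mild-anemia band: "Hb 10.0 – 10.9 in pregnant women and children".
- **Who decides.** Sections 5.6 and 8.2 leave treatment decisions to local health workers and facilities.

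**The concern.** A referral table should agree with the protocol's own description of the recommendation that it relays. Two rows of Table 5 name a course that includes primaquine for any participant with confirmed malaria, while two other sections say that the recommendation does not extend to pregnant women. Staff who followed the table literally for a pregnant, vivax-positive participant would issue a referral at odds with sections 1.0 and 5.4. The accuracy endpoints are unaffected. What is at stake is the consistency of a safety-relevant instruction, and whether staff can tell when the exception applies.

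**Working it through.** No arithmetic applies, and the plan gives no figure to reproduce. The check compares the texts.

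**Step 1. Which part of the exception matters here.** It names two groups: pregnant women and infants under six months. The minimum age of 2 years removes the infants. Only pregnancy remains.

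**Step 2. Whether pregnant women can enter.** Neither eligibility list excludes them. The anemia band for pregnant women is consistent with their inclusion. It is one line of a general threshold list, though, so eligibility rests on the absence of an exclusion.

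**Step 3. Side-by-side reading for a vivax-positive pregnant participant.**

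| POC result | Table 5 | Section 5.4 | Agrees with the stated exception? |
|---|---|---|---|
| Normal | Referral naming chloroquine and 7 days of primaquine | No POC result notified (unless already known deficient or intermediate from earlier studies) | No: course named without qualification |
| Intermediate | Same course, plus counselling and monitoring | Team recommends that primaquine be closely monitored | No: both texts presuppose primaquine |
| Deficient | Chloroquine, with primaquine withheld pending confirmation | Same; if the reference assay reads normal, referral for liver-stage treatment under national guidelines | No unqualified primaquine course at referral |

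The intermediate row is the sharper conflict for two reasons. The study adds its own message there, and that message assumes that primaquine is given. Also, Table 2 (section 3.2) defines the intermediate class for females only, although section 5.4 states the 30 to 80% band without reference to sex.

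**Step 4. Whether staff would know pregnancy status.** The point-of-care procedures in section 5.2.4 include no pregnancy question or test. The visible plan has two rules that turn on pregnancy: the primaquine exception and the anemia band. On the section 5.6 bands, mild anemia is 10.0 to 11.9 g/dl in women and 10.0 to 10.9 g/dl in pregnant women. A hemoglobin of 11.0 to 11.9 g/dl is therefore classified differently according to a fact that no visible step records.

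**Step 5. Size.** A count would need the number of women of childbearing age, the proportion pregnant, and the proportion vivax-positive. The documents give none of these. The expected 200 intermediate participants among 2,000 are not restricted to malaria cases and do not help. About half the sample are household recruits rather than febrile clinic patients (section 4.1), so one positivity rate could not be applied to everyone.

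**The case against.** The strongest reply is that these rows are referrals, not treatment orders. The health system decides, and the protocol itself describes that system's recommendation as carrying the exception. On this view Table 5 uses the standard course as shorthand, and a POC-normal woman is sent for the care she would have received without the study. Most of this stands, and it limits the weight of the point. It does not remove the inconsistency. The table names a specific course, whereas section 5.4 elsewhere refers to national guidelines for participants found normal by the reference assay. In the intermediate row the study adds its own recommendation.

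A reader might infer that a normal POC result would serve as clearance for primaquine. The documents do not support that. Section 5.4 limits disclosure of G6PD results to participants found intermediate or deficient, or whose earlier result needs correcting, and no visible step sends a normal POC result to the prescriber. Section 8.1 speaks of treatment informed by G6PD status, but only in general terms.

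It is also fair to object that Figure 3, the data form (Appendix A1), and the counselling and results-return materials (Appendices C2 and C3) cannot be seen. Section 5.4 says staff counsel from the script in C3, so Table 5 may not be the only text that they use. Pregnancy may be handled in those materials. This stands as a condition on the finding, which covers the visible text only.

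**Conclusion.** The point holds as an internal inconsistency. Two rows of Table 5, the guideline summary in section 5.6, and the monitoring recommendation in section 5.4 do not carry the pregnancy exception that sections 1.0 and 5.4 themselves state, and pregnant women are not excluded from the study. Its weight is limited because prescribing lies outside the study, but it bears on participant safety and should be corrected.

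A reader might infer that the study gives primaquine to pregnant women, or that a known number would be affected. Neither follows: the study refers and does not treat, and no count can be derived from the documents. The conclusion assumes that silence in the eligibility criteria means eligibility, and that the unseen figure and appendices do not already resolve the conflict.

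**What to change.** Reconcile Table 5, the guideline summary in section 5.6, and the POC-intermediate text in section 5.4 with the exception in sections 1.0 and 5.4. Check Figure 3 and the results-return script (Appendix C3), and align them if they carry the same wording. The investigators should state which rule applies; this review does not propose one.

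Unless Appendix A1 already does so, add self-reported pregnancy to the data form, so that the plan's own pregnancy-dependent rules (the primaquine exception and the anemia band) can be applied.

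The cost is a wording change and at most one form item. The sample size and the accuracy analysis do not change.

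### For vivax-positive participants who read POC normal (status not previously known) or POC intermediate, the visible text states no step to withhold or stop primaquine when the reference assay later reads below 30%

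*Combined protocol and SAP*

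**What the plan says.** The malaria rows of Table 5 (section 5.6) set the action by POC reading. POC normal and POC intermediate are both referred for 3 days of CQ and 7 days of PQ; POC intermediate adds counselling and advice to watch for hemolysis. For a later reference result, both rows say: "If confirmed deficient or intermediate with reference assay, provide follow up counselling as described above". The earlier G6PD rows of the table define that counselling by pointing to Appendix C2. Section 5.4 describes Appendix C2 as a card for patients and providers covering contraindicated medicines and other risk factors such as foods.

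For POC-deficient participants, section 5.4 says "the study team will provide referral with the recommendation that primaquine treatment be withheld until confirmatory testing can be completed", and Table 5 has the matching "recommendation for health care provider to withhold PQ until confirmatory G6PD testing".

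For POC intermediate, section 5.4 gives two reference outcomes. One is agreement: "If the results of the reference assay confirm the results of the POC G6PD test (enzymatic activity between 30-80%) they will be contacted". The other is a normal reference result, where "they will be contacted and informed of the result and referred to a health agent to receive with standard treatment for liver stage disease". A vivax-positive participant already known to be deficient or intermediate who reads POC normal is handled as if the POC test had read deficient or intermediate.

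**The concern.** A participant of unknown status who reads POC normal, or any participant who reads POC intermediate, can be below 30% on the reference assay. The study then holds a result that bears on a PQ course it has just referred the person to receive. Section 5.4 separates the two abnormal categories (no standard PQ if deficient, close monitoring if intermediate), but these two Table 5 rows merge them into one counselling action. A correction to normal comes with a referral back to a health agent; a correction to below 30% has no such step written. The event at stake is severe hemolysis in a participant whom the study knows to be deficient.

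**Working it through.** This is a question of procedure text, so there is no planned figure to reproduce. I set the rules side by side, then checked timing and scale.

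**Stated actions, vivax-positive participants (section 5.4 and Table 5)**

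| POC reading | At the visit | Reference below 30% | Reference 30-80% | Reference normal |
|---|---|---|---|---|
| Deficient | CQ; PQ held until confirmation | Contacted, informed; counselled, including on future PQ | Counselled according to status | Contacted; referred for liver-stage treatment |
| Intermediate | CQ and PQ, with monitoring advice | No branch in 5.4; counselling in Table 5 | Contacted, informed; counselled | Contacted; referred for standard treatment |
| Normal, status unknown | CQ and PQ | No specific paragraph in 5.4; counselling in Table 5 | Same as below 30% | No further action |
| Normal, previously known deficient or intermediate | Handled as POC deficient or intermediate | As those rows | As those rows | As those rows |

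The gap is the below-30% cell in the second and third rows. Previously known deficient participants who read POC intermediate also fall in the second row, because the known-status exception covers only those who read POC normal. Table 5 says confirmed malaria; the restriction to vivax comes from the text of sections 5.4 and 5.6.

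**Timing.** Section 5.6 puts PQ after 3 days of CQ. With the visit as day 1, CQ runs on days 1-3 and PQ on days 4-10.
- At the 72-hour limit for refrigerated storage before testing (section 5.3), the result falls on day 4: 0-1 of 7 doses taken.
- At one week, the confirmatory limit that section 5.4 states for POC-deficient participants: 4 doses taken by the end of day 7 and 3 left (5 and 2 by the end of day 8).
- If PQ instead started on day 1 (assumption), 4 doses would remain after day 3 and none after day 7.

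The 24-hour limit in section 5.2.5 is written for hemoglobin. The reference assay is to run at the same time, but no turnaround for its result is given there, and discrepant replicates are repeated. I therefore do not use 24 hours as the result time.

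**Scale.** Expected number = deficient participants x vivax share x (1 - POC sensitivity at 30%).
- Clinic group: half of 2,000 (section 4.1) = 1,000; x 5% prevalence (section 3.2) = 50 deficient.
- Vivax share: not given; assumed 10-40%, so 50 x 0.10 = 5 to 50 x 0.40 = 20.
- Sensitivity: 100%, lower limit 95.1% (Table 7), so the share read too high is 0-4.9%. Result: 0 to 20 x 0.049 = 0.98.
- Household group, only those reading POC intermediate: 100 expected deficient less 50 = 50 (assumption, since the sample is enriched); x 0-5% vivax positive (assumption) = 0-2.5; x 0.049 gives at most 0.12.
- Total: 0 to 0.98 + 0.12 = 1.10.

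Varying the assumptions: a 50% clinic vivax share gives 25 x 0.049 = 1.2. A sensitivity of 90% (assumption) with a 40% share gives 20 x 0.10 = 2. Most affected participants would read POC intermediate, because a POC-normal reading means missing the whole 30-80% band.

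**The case against.** The strongest reply is that the instruction may sit where it cannot be seen. Figure 3 (participant flow), Appendix C2 (the card) and Appendix C3 (the results-return script) are not visible. The card is meant for providers as well as patients and covers contraindicated medicines, and primaquine is the drug this protocol is about. That stands, and it is why the fix allows a cross-reference. It does not remove the point: the rows that staff will follow give one action for two results that section 5.4 treats differently.

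Other parts of the reply also stand. Every participant found deficient or intermediate is to be contacted and counselled, and section 9.0 tracks delivery of counselling and cards, though not provider notification or whether PQ was stopped. POC-intermediate participants already get hemolysis-monitoring advice. Section 5.6 says "The participant's G6PD status will then be confirmed by a reference assay to inform further case management as necessary"; that paragraph opens with POC-deficient participants, but its counselling message also mentions intermediate status. Standard care gives PQ with no G6PD test, and treatment decisions rest with the health system.

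A reader might infer that the plan answers a confirmed deficient result more weakly than an unconfirmed one. The documents do not support that comparison. Withholding PQ is an interim hold for POC-deficient participants pending the reference result; once it confirms deficiency, their stated action is also contact and counselling. The difference is that their row names PQ and the other two do not.

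A reader might also infer that the result will usually arrive before the first PQ dose. The 24-hour figure belongs to hemoglobin, and the one-week limit in section 5.4 allows a later result.

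**Conclusion.** The gap holds on the visible text, as a minor safety point. A PQ course could continue in a participant whom the reference assay has shown to be deficient, with nothing in these rows or in section 5.4 directing a withhold-or-stop recommendation to the treating health agent. Counselling could still lead to stopping PQ in practice.

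The expected number is about 0-1 participant, and 0 at Table 7's point estimate. This rests on assumed vivax shares, an assumed split of deficient participants between the two recruitment groups, and a sensitivity from 314 stress-test data points at an optimised cut-off of 4.2 U/gHb; the field cut-off in U/gHb is not given. No endpoint, estimate or analysis is affected. A stop recommendation would still be useful at 72 hours and, with PQ after CQ, at one week. Confidence is medium because Figure 3 and Appendices C2 and C3 could not be read.

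**What to change.** In section 5.4, and in the POC-normal and POC-intermediate malaria rows of Table 5, add one rule: when the reference assay reads below 30% in a vivax-positive participant, the study team promptly notifies the participant and the treating health agent, before the first PQ dose where possible, and recommends that PQ be withheld or stopped. State that the treatment decision stays with the health system.

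If Figure 3, Appendix C2 or Appendix C3 already says this, cite it in those two rows instead.

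The cost is protocol wording in two places and one provider message for an expected 0-1 participant. The assay and the contact with the participant are already planned, so no extra test or visit is needed.
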